Descriptive statistics will be performed for demographic variables. Categorical variables will be reported as n (%) and will be analyzed by chi-square or Fisher's exact test as appropriate. Continuous variables will be reported as mean with standard deviation or median with interquartile range and analyzed by repeated measures ANOVA or non-parametric equivalent based on the normality of the data distribution. Analyses will be performed at each time point for the primary and secondary outcomes as the dependent variables and group assignment and time point (visit number) as factors. Paired t test or non-parametric equivalent may also be used for within group comparisons. Statistical analysis will be performed using IBM SPSS statistics version 24.0 and the level of significance set at p less than 0.05, two-sided.

Primary outcome analysis will be intention to treat at the 12 month time point. Per-protocol analysis will also be reported. Primary outcome will be reported as change from the PRTEE baseline score to the 12 month PRTEE score. The minimally clinically important difference (MCID) on the PRTEE is considered to be 10, and will be used as the benchmark for success of the treatment protocol. The primary outcome variable will be the comparison of the change in PRTEE in the intervention group, compared to the control group. Missing data will be dealt with after evaluation of the cause of the missingness; and potential strategies include complete case analysis, multiple imputation model, and inverse probability weighting.

RCT of standard PT vs. PT and BFR for the treatment of LE

Secondary outcomes will be comparison of the change in the NPRS between groups; change in 1 repetition maximum between groups; and change in grip strength between groups.

Multiple linear regression analysis will be performed to control for the effects of age, sex, length of condition, previous and current treatments, occupation on change in PRTEE from baseline to 3, 6 and 12 months.

Power Analysis

A two sample t test of normal mean difference assuming a group standard deviation of 10 PRTEE score points based on findings by Krogh, et. al. (2013)²⁴, a minimal clinically important difference of 10²⁵, a two-sided significance of 0.05, and a power of 80% resulted in a sample size of 17 per group. A dropout rate of 30% is expected, thus the plan is to recruit a total of 22 patients per group for a total of 44 subjects.

Ethical Considerations

Risks and Side Effects

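### The named repeated measures ANOVA and the deferred missing-data method leave open a complete-case primary analysis, which would contradict the promised intention-to-treat analysis at 12 months

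*Combined protocol and SAP*

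**What the plan says.** All of this is in the combined protocol and SAP.

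- **Model.** Under Statistical Analysis, continuous variables are to be "analyzed by repeated measures ANOVA or non-parametric equivalent based on the normality of the data distribution". Group and time point are the factors, and the software is SPSS. Apart from a supplementary multiple regression, this is the only between-group method named for continuous outcomes.
- **Analysis set.** The same section states: "Primary outcome analysis will be intention to treat at the 12 month time point". The primary outcome is the PRTEE change from baseline to 12 months, compared between groups. A per-protocol analysis is also to be reported.
- **Missing data.** "Missing data will be dealt with after evaluation of the cause of the missingness". Multiple imputation, inverse probability weighting and complete cases are listed as possibilities. None is named as primary.
- **Expected loss.** Under Power Analysis: "A dropout rate of 30% is expected". No rate is given for missed interim assessments.
- **Schedule.** Under Data Collection, PRTEE is taken at entry, at the sixth or last therapy visit, and by emailed survey at 3, 6 and 12 months. That makes five assessments.

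**The concern.** Conventional repeated measures ANOVA needs a complete row for each patient. Someone who answers at baseline and 12 months but misses the 3-month survey is deleted, although the 12-month score exists. Unless the data are first imputed, the analysis is restricted to patients complete at every visit, which is not an analysis of everyone randomised.

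The plan does not close that route. The missing-data method follows an evaluation of why data are missing, so it is chosen after the pattern of loss is known, and complete-case analysis is an allowed answer. The observed data alone cannot show whether loss depends on the unseen scores, so the rule fixes nothing in advance. The switch to a non-parametric method on observed normality adds a second data-dependent choice.

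Two things are at stake. One is precision in a trial of 44. The other is bias: the trial is open label with a self-reported primary outcome, so loss related to arm or response is plausible. The documents give no dropout by arm and no outcomes in those lost, so the bias cannot be sized from them. The loss of patients and power can.

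**Working it through.** **Inputs, all from Power Analysis.** Difference 10 points; SD 10 ("assuming a group standard deviation of 10 PRTEE score points"); "a two-sided significance of 0.05, and a power of 80"%; dropout 30%; "the plan is to recruit a total of 22 patients per group for a total of 44 subjects".

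**Step 1: reproduce the plan's figure.** For a two-sample t test with n per group, the noncentrality is (10/10) × √(n/2) on 2n − 2 degrees of freedom. Solving for 80% power gives n = 16.7, so 17 per group (power 80.7%). This matches the plan's "a power of 80% resulted in a sample size of 17 per group".

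**Step 2: complete cases at the stated dropout.** Read the 30% as patients with no 12-month PRTEE, and assume no other missing data. Then 44 × 0.70 = 30.8 patients, or 22 × 0.70 = 15.4 per group. The noncentrality is √(15.4/2) = 2.77 and power is about 76%.

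**Step 3: add missed interim assessments.** The documents give no rate, so this is an assumption. Let a proportion q be missing independently at each of the three interim assessments (final therapy visit, 3 months, 6 months). The fraction complete at every visit is 0.70 × (1 − q)³.

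| q (assumed) | Fraction complete | Patients of 44 | Per group | Power |
|---|---|---|---|---|
| 0 | 0.700 | 30.8 | 15.4 | 76% |
| 5% | 0.70 × 0.857 = 0.600 | 26.4 | 13.2 | 69% |
| 10% | 0.70 × 0.729 = 0.510 | 22.5 | 11.2 | 62% |
| 15% | 0.70 × 0.614 = 0.430 | 18.9 | 9.5 | 54% |

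Power is the two-sample t test value at the expected number per group. Rows below the first apply only when the model uses all five assessments. A plain comparison of baseline-to-12-month change on observed data stays at the first row, whatever happens at interim visits.

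**Step 4: what losing half would need.** Setting 0.70 × (1 − q)³ = 0.50 gives q = 1 − (0.5/0.7)^(1/3) = 10.6% at each interim assessment.

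**Step 5: separate the two shortfalls.** The 76% is already below 80% because 17 × 1.3 = 22.1 was used as the dropout allowance, and 22 × 0.70 = 15.4 is short of 17. That is a sample-size matter. The loss attributable to deleting patients for missed interim visits is the drop from 76% down the table.

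**The case against.** The strongest reply is that a five-visit ANOVA may not be the primary analysis at all. The ANOVA sentence covers continuous variables generally. The primary outcome is described as a change from baseline to 12 months, analyses are promised at each time point, and the sample size rests on a t test. With only two time points, the group-by-time test is the same as a t test on change, and interim gaps do not matter. This reading is as open as the other. It does not remove the problem: patients without a 12-month score still drop out unless a method is fixed, and two defensible readings mean the primary analysis is not settled.

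Four stronger statements might be inferred, and the documents do not support them:

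- *The intention-to-treat analysis will become a complete-case analysis.* Imputation and weighting are both listed, and ANOVA on imputed data would keep all 44. The defect is that the choice is deferred.
- *About half the patients will be lost.* The stated 30% leaves about 70%. Half needs the 10.6% in Step 4, and independence. If those who miss interim surveys are mostly those lost by 12 months, completers stay near 31. Up to three emails and three calls per follow-up point also limit interim loss, although the final-visit score is collected only if that visit is known to be the last.
- *The non-parametric fallback cannot compare groups.* That would be true of the Friedman test, but the plan does not name it. For change at one time point a Mann-Whitney test would serve.
- *The choice is open to manipulation.* The Blinding section has the final analyst blinded to allocation, which reduces that risk. It does not replace pre-specification.

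**Conclusion.** The concern holds in limited form. The plan permits a complete-case repeated measures ANOVA as its primary analysis, and that would contradict its intention-to-treat statement. On that route at most about 31 of 44 patients are expected in the analysis, with power about 76%. Under assumed independent interim missingness of 5% to 15% per visit, this falls to between 26 and 19 patients and power of 69% to 54%. The first figure rests on the plan's own difference, SD and dropout, with dropout read as no 12-month PRTEE. The rest depends on interim rates that the documents do not give. The plan does not commit to this route, but nothing in it rules the route out. Because it concerns the primary estimate, it should be settled before outcome data are seen.

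**What to change.** For the primary endpoint, replace the ANOVA and the normality switch with one pre-specified, likelihood-based mixed model for repeated measures (SPSS MIXED):

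- **Outcome:** PRTEE at the final therapy visit, 3, 6 and 12 months.
- **Fixed effects:** arm, time, arm-by-time, baseline PRTEE and site. Envelopes are issued in blocks by site, so site belongs in the model.
- **Covariance:** unstructured, with a named simpler structure if it does not converge, given the small sample; Satterthwaite degrees of freedom.
- **Patients:** all randomised patients with any follow-up, in the arm assigned.
- **Primary estimate:** the arm difference at 12 months with 95% CI. With baseline in the model, this is also the adjusted difference in change, so the endpoint is unaltered.

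Name in advance one sensitivity analysis that includes all 44 randomised patients: multiple imputation with a delta shift. It is needed because the mixed model omits patients with no follow-up and assumes data are missing at random. State that the multiple regression is supplementary.

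Pre-specified multiple imputation followed by a baseline-adjusted comparison at 12 months would also be sound. The mixed model is preferred because it uses partial follow-up directly.

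The cost is small: a change to the statistical wording, with the same data and software, and reliance on the missing-at-random assumption, which the sensitivity analysis tests.

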Once patients have consented to participation, subjects will be randomly assigned to either intervention or control group-both consisting of 22 patients. Consent will be obtained by referring physicians, or physical therapists at approved sites participating in the study [further details regarding consent procedure below]. At all physical therapy sites participating in the study, patient service representatives will be trained in the study recruitment, collecting patient enrollment paperwork and other clerical needs. Allocation will occur in blocks of 4 by opaque envelope. The envelopes will be generated by web based randomization software²¹ placed into opaque, sequentially numbered envelopes and delivered to participating physical therapy clinics prior to beginning recruitment. Two sites will contain 4 blocks of 4 envelopes, and one site will contain 3 blocks of 4, ensuring a total of 44 patients. If one site or another enrolls more patients, only a full block of 4 envelopes will be transferred to that site for further enrollment. The envelopes will be stored in the desk of the directing physical therapist at each location,

and only removed once a patient has been enrolled. Once patients consent to enroll in the study, they will receive the next envelope in sequence in the group of 4, and be allocated to either the intervention or control group. The envelope will contain a number which the treating physical therapist will then compare to the master allocation list, which will reveal which treatment group #1 or #2(intervention or control) the patient has been allocated; it will also contain the patient's assigned identification number (PID). The treating physical therapist will be responsible for communicating the subject's allocation and PID which will be contained in their envelope to the primary investigator, who will hold the confidential master list. Outcomes data will be collected in a separately in REDCap.

Blinding

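### No planned model adjusts the 12-month PRTEE comparison for baseline PRTEE or site; the change-score analysis is valid, but adding them would usually gain precision at almost no cost

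*Combined protocol and SAP*

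**What the plan says.** All references are to the combined protocol and SAP.

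- **Primary endpoint and contrast (Statistical Analysis).** "Primary outcome will be reported as change from the PRTEE baseline score to the 12 month PRTEE score", and "The primary outcome variable will be the comparison of the change in PRTEE in the intervention group, compared to the control group".
- **Main model (Statistical Analysis).** Repeated measures ANOVA or a non-parametric equivalent, with "group assignment and time point (visit number) as factors".
- **Additional regression (Statistical Analysis).** The purpose of a multiple linear regression is given as: "control for the effects of age, sex, length of condition, previous and current treatments, occupation on change in PRTEE from baseline". It covers all three later follow-up times. It is not named as the primary analysis, and its list contains neither baseline PRTEE nor site.
- **Sample size (Power Analysis).** "A two sample t test of normal mean difference", with a standard deviation of 10, a difference of 10, two-sided 0.05 and 80% power, gives 17 per group. With 30% dropout expected, 22 per group are recruited. The text does not say whether 10 is the SD of a score or of a change.
- **Randomisation (Randomization/Allocation).** "Allocation will occur in blocks of 4 by opaque envelope". The section then divides the envelopes among the sites: "Two sites will contain 4 blocks of 4 envelopes, and one site will contain 3 blocks of 4, ensuring a total of 44 patients". Only full blocks may move between sites, so allocation is in effect stratified by site.

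**The concern.** Baseline PRTEE is measured on everyone but enters the primary comparison only by subtraction. Subtraction fixes the coefficient of baseline at 1. If the true slope of 12-month on baseline PRTEE is not 1, two things follow. The estimate has a larger variance than one that fits the slope, and in the trial actually run, part of any chance baseline difference between the arms stays in the treatment effect.

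The other planned analyses do not close the gap. With baseline and 12 months as the two time points, the group-by-time test in a repeated measures ANOVA is the same as the change-score test. The covariate regression omits the variable most directly tied to the endpoint.

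The trial is small and has little power to spare, so lost precision matters. The arms may also differ noticeably at baseline by chance.

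**Working it through.** **Inputs from the documents:** difference 10, SD 10, two-sided 0.05, 17 per group evaluable, 22 per group recruited, 30% dropout, three sites.

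**Assumptions, because the documents give no figure:** r, the correlation of baseline with 12-month PRTEE, is taken as 0.3, 0.5 and 0.7. The ratio k = SD(12 months)/SD(baseline) is taken as 1, then 1.25. SD 10 is read both ways.

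**1. The plan's own figure.** The noncentral t calculation for a two-sample test with difference/SD = 1 gives 16.71, so 17 per group, with 80.7% power. The stated figure reproduces. After 30% loss, 22 × 0.7 = 15.4, or about 15 per group. Unadjusted power there is 75.3% if the SD of change is 10.

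**2. Variance.** Take the baseline variance as 1.
- Change score: 1 + k² − 2rk.
- ANCOVA residual: k²(1 − r²).
- With k = 1 the ratio ANCOVA/change is (1 − r²)/(2(1 − r)) = (1 + r)/2. This is 0.65, 0.75 and 0.85 at r = 0.3, 0.5 and 0.7, or 35%, 25% and 15% lower.

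**3. Power at 15 per group, k = 1.** Noncentral t; the adjusted model loses 3 further degrees of freedom (1 for baseline, 2 for site). Site is assumed to explain no variance.

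| r | Change SD 10: unadjusted | Change SD 10: adjusted | Score SD 10: unadjusted | Score SD 10: adjusted |
|---|---|---|---|---|
| 0.3 | 75% | 90% | 61% | 79% |
| 0.5 | 75% | 86% | 75% | 86% |
| 0.7 | 75% | 81% | 93% | 96% |

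Under the score reading, the SD of change is 10√(2(1 − r)) and the ANCOVA residual SD is 10√(1 − r²).

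**4. Unequal SDs.** With k = 1.25 and change SD 10:
- r = 0.5: ratio = 1.5625 × 0.75 / (2.5625 − 1.25) = 1.172/1.3125 = 0.89; adjusted power about 80%.
- r = 0.7: ratio = 1.5625 × 0.51 / (2.5625 − 1.75) = 0.797/0.8125 = 0.98; adjusted power about 76%.

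Both compare with 75% unadjusted.

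**5. Small-sample cost not in steps 3 and 4.** Estimating the slope inflates the ANCOVA variance by about 1/(N − 4) on average. With 30 completers this is 1/26, or about 4%. It takes roughly 1 to 2 points off each adjusted power figure, enough to cancel the gain where the ratio is 0.98.

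**6. Chance imbalance.** The slope is b = r × k. A baseline difference D between the arms shifts the change contrast by (b − 1) × D. If the baseline SD is 10 (assumed), the standard error of D is 10√(2/22) = 3.0 points at 22 per group. With b = 0.5, a 3-point difference shifts the estimate by 1.5 points, which is 15% of the 10-point target. A 5-point difference shifts it by 3.5, 2.5 or 1.5 points at b = 0.3, 0.5 or 0.7.

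**7. Site alone, at 17 per group.** If site explains no outcome variance, adjusting for it moves power from 80.7% to 80.5%. If it explains 5% or 10% (assumed), power becomes 82.5% or 84.5%.

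**The case against.** The strongest reply is that nothing here is invalid. In a randomised trial the change-score comparison is unbiased over randomisations and keeps its type I error. A reader might infer that the primary result would be biased by regression to the mean. The documents do not support that: the shift in step 6 is conditional on the imbalance that happens to occur and averages to zero.

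A reader might also infer that subtraction over-corrects whenever r is below 1. It does not. The quantity that matters is r × SD(12 months)/SD(baseline). With r = 0.7 and a ratio of 1.43 the slope is 1, and subtraction is the right correction. The documents give neither r nor the SDs by time point, so the size of the gain is uncertain and could be close to nothing.

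On site, a reader might infer that leaving out a stratifying factor biases the estimate. The site blocks already roughly balance the arms within site. Omitting site costs at most a conservative standard error, and the gains in step 3 come from baseline, not site.

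Finally, the plan does intend covariate adjustment through its regression. That is true, but the listed covariates do not include baseline PRTEE or site, and the regression is not the primary analysis.

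These points limit the severity and size of the concern. They do not remove the gap or provide a reason to leave it.

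**Conclusion.** The point holds as something that should be fixed, not as a fault that invalidates the trial. The primary analysis uses raw change, and no planned model adjusts for baseline PRTEE or site. Apart from the small cost of estimating the extra terms, ANCOVA is never less precise than the change score.

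For r between 0.3 and 0.7 and equal SDs, the variance falls by 35% to 15%. At 15 completers per group with change SD 10, that moves power from 75% to between 90% and 81%. If 10 is the SD of a score, the gain runs from 18 points at r = 0.3 (61% to 79%) to 3 points at r = 0.7 (93% to 96%). If the 12-month SD is 1.25 times the baseline SD, the gain with change SD 10 is about 5 points at r = 0.5 and negligible at r = 0.7.

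It would be too strong to say that adjustment guarantees 80% power after the expected dropout. That depends on values the documents do not give. Site adjustment is secondary.

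**What to change.** In the Statistical Analysis section:

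1. Name as the primary analysis a linear model of 12-month PRTEE on group, baseline PRTEE and site (three-level fixed effect). Report the adjusted group difference with its 95% confidence interval.
2. Use the same form, with each outcome's own baseline and planned time point, for NPRS, maximum grip strength, maximum pain-free grip strength and 1 repetition maximum.
3. Add baseline PRTEE to the multiple regression already planned, and label that regression as supportive.
4. Report raw change by group descriptively.
5. In Power Analysis, say whether the SD of 10 refers to a score or to a change.

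The cost is SAP wording and 3 degrees of freedom. The baseline measures are already collected. Site is not in the baseline list under Data Collection but is known from where the envelope was opened, so it only needs recording. The wording should be fixed before outcome data by group are seen, so that nobody can later choose between adjusted and unadjusted estimates.

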 - a. We will also collect this data at final in person therapy visit, 3 months, and 6 months from baseline. These will be considered secondary outcomes.

Secondary Outcomes:

1. Change in Numeric pain rating scale (NPRS) from baseline visit to 12 months.
2. Change in maximum pain free grip strength from baseline to final therapy visit.
3. Change in maximum grip strength from baseline to final therapy visit
4. We will provide descriptive statistics as to whether subjects have sought other treatment after finishing our treatment protocol. This data will be collected as part of the 3, 6, 12 month contacts.
 - a. Other treatments sought will include: further doctor's visits, oral medications prescribed, injection therapy (and what type), surgical treatment.

The NPRS and PRTEE are validated, standardized outcome measures commonly used when assessing lateral epicondylitis. Assessing grip strength is standard practice, however, we wished to differentiate between maximum grip strength vs pain limiting grip strength.

Long Term Goals

The long term goals depend somewhat on the outcome of the trial. If the new BFR device shows promise and is seen to be superior to standard therapy, there is potential to evaluate its use in multiple types of chronic degenerative tendinopathy. There is also the potential to decrease the number of patient visits to therapy offices, increasing the value of therapy if it is effective. We also see the potential to apply to other degenerative conditions such as osteoarthritis to see if there is potential to improve therapy techniques and benefits for conditions such as these.

Research Design and Methods

Brief Design Description

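### The missing-data method for the 12-month PRTEE primary is chosen only after the missingness is seen, so with 30% dropout expected the declared intention-to-treat analysis is not assured

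*Combined protocol and SAP*

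**What the plan says.** All references are to the combined protocol and SAP.

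- **Statistical Analysis, analysis set:** "Primary outcome analysis will be intention to treat at the 12 month time point". The comparison is defined as: "The primary outcome variable will be the comparison of the change in PRTEE in the intervention group, compared to the control group". The only second analysis named is the per-protocol one: "Per-protocol analysis will also be reported".
- **Statistical Analysis, missing data:** "Missing data will be dealt with after evaluation of the cause of the missingness; and potential strategies include complete case analysis". The list in full: "potential strategies include complete case analysis, multiple imputation model, and inverse probability weighting". The section gives no order of preference, rule for choosing, imputation or weighting model, date for fixing the choice, or sensitivity analysis for missing data.
- **Statistical Analysis, model:** continuous outcomes are analysed by repeated measures ANOVA or a non-parametric equivalent, in SPSS 24.
- **Power Analysis:** "A dropout rate of 30% is expected"; 17 evaluable per group, 22 recruited.
- **Outcomes:** on the PRTEE, "We will also collect this data at final in person therapy visit, 3 months, and 6 months from baseline".
- **Blinding:** patients and therapists know the treatment; the analyst is blinded to allocation.

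**The concern.** Complete case, multiple imputation and inverse probability weighting are not interchangeable. They rest on different assumptions and can give different answers from the same 44 patients. The plan defers the choice to an evaluation of why data are missing, but that evaluation cannot settle it: observed data can show whether dropout is related to earlier PRTEE, not whether it also depends on the 12-month score that was never seen.

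Intention to treat is declared, but how a randomised patient without a 12-month score enters the analysis is not. Under complete case that patient is dropped. Classical repeated measures ANOVA needs a full record across its time points, so unless imputation comes first it pulls the same way. In both cases the patient's final-visit, 3-month and 6-month PRTEE go unused.

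The trial is open label with a self-reported primary outcome, so different reasons for leaving in the two arms are plausible. The stake is a biased 12-month difference, with a method that cannot be shown to have been fixed beforehand.

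**Working it through.** **Inputs from the plan (Power Analysis):** difference 10, SD 10, two-sided alpha 0.05, power 80%, 22 recruited per arm, dropout 30%. **Assumed, because the documents give nothing:** correlation between earlier and 12-month PRTEE, and the dropout mechanism.

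**1. The plan's own figure.** Two-sample t test, noncentrality = 10 / (10 × √(2/n)) = √(n/2). At n = 17 this is √8.5 = 2.92 and power is 80.7%; at n = 16 power is 78.1%. So 17 per group reproduces.

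**2. Patients affected.** 44 × 0.30 = 13.2 without a 12-month score; 22 × 0.70 = 15.4 per arm remain.

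**3. Complete-case power under random dropout.**

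| Completers per arm | Power |
|---|---|
| 15 v 15 | 75.3% |
| 15 v 16 | 76.7% |
| 16 v 16 | 78.1% |

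Using the earlier visits lowers the standard error by only about 3% to 7% in this setting.

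**4. Size of complete-case bias, by algebra.** With dropout fraction d, the mean of all patients in an arm = observed mean + d × (missing mean − observed mean). If d is the same in both arms, the complete-case error in the treatment difference therefore has size d × G, where G is the between-arm difference in that missing-minus-observed gap. At d = 0.30:

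| G (assumed), PRTEE points | Bias, points |
|---|---|
| 5 | 1.5 |
| 10 | 3.0 |
| 15 | 4.5 |
| 20 | 6.0 |

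**5. Simulation under no treatment effect** (22 per arm, SD 10). The log-odds of a missing 12-month score change with an earlier PRTEE value, upward in one arm and downward in the other.

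| Slope per SD; missing | Correlation | Complete-case bias, points | Complete-case false positives | Imputation using the earlier value |
|---|---|---|---|---|
| 1.0; about 31% | 0.5 to 0.7 | 2.6 to 3.8 | 11% to 17% | bias near 0; 4% to 5% |
| 0.8; about 30% | 0.7 | 3.1 | 13.8% | 3.8% |
| 0.8; about 30% | 0.5 | 2.1 | 8.3% | 4.1% |
| 0.8; about 30% | 0.3 | 1.3 | 6.3% | 4.6% |

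The first row agrees with step 4: 2.6 / 0.31 = 8.4 and 3.8 / 0.31 = 12.3, so it corresponds to G of about 8 to 12 points.

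When dropout was random, or depended on earlier PRTEE in the same way in both arms, complete case was unbiased (within 0.06 points) and every method rejected in about 4% to 5% of runs.

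In the slope-0.8 runs, inverse probability weighting with no arm-by-PRTEE term in the weighting model still rejected in 5.5%, 7.5% and 11.7% at correlations 0.3, 0.5 and 0.7. Naming weighting without its model is therefore not enough.

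**Limit of step 5:** the earlier PRTEE is taken as seen for everyone. Patients lost before 6 months would be corrected less well.

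**The case against.** The plan shows more care than many of its size. It declares intention to treat, lists recognised methods, ties the choice to the cause of missingness rather than to results, blinds the analyst, and (Data Collection) provides three emails and up to three calls per time point. It also says analyses are done at each time point and sizes the trial on a two-sample t test, so a plain 12-month comparison need not delete anyone for missing an earlier visit. The bias figures need a dropout pattern that no document predicts.

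Much of this stands, and it rules out several stronger readings:

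- **That the primary is not intention to treat.** A reader might infer this. Two of the three options aim at all randomised patients; only a complete-case choice drops them. The set is unassured, not abandoned.
- **That complete case is the default because it is listed first.** The plan calls all three potential strategies and ranks none.
- **That the open choice inflates the false-positive rate.** In simulation at least one of the three methods was significant in about 6% to 7% of null trials when missingness did not differ by arm, and in more when it did. That requires running all three and reporting the smallest p-value, which the plan does not propose. It is a ceiling on misuse, not the plan's error rate.
- **That listwise deletion cuts power to 62%.** 22 × 0.7 × 0.9³ = 11.2 per arm gives that figure, but the 10% miss at each of three earlier follow-ups, independent of each other and of 12-month dropout, is assumed. Clustered misses would leave more complete records.

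What the objection does not remove: analyst blinding does not prevent seeing which method separates the coded groups, it does nothing for complete-case bias, and nothing else in the document fixes the method.

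**Conclusion.** The concern holds in this form: the primary missing-data method is open until the missingness is seen, no rule closes it, and intention to treat is therefore not assured for about 13 of 44 patients.

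Under random dropout the cost is small. Power of 75% to 78% rather than 80% mostly reflects having about 15 completers per arm instead of 17, and a better missing-data method recovers little of it.

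The material risk is bias: about 2.6 to 3.8 points against an MCID of 10, with 11% to 17% false positives under no effect. This is conditional on dropout acting in opposite directions by arm, about 31% missing and correlation 0.5 to 0.7. With a weaker mechanism or lower correlation it shrinks; without arm-dependence it disappears. The documents neither support nor exclude that pattern. The case for acting is that the data which protect against it are already being collected.

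**What to change.** Before data lock, replace the missing-data sentence with one fixed rule:

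- **Primary:** a likelihood-based mixed model (SPSS MIXED) for PRTEE at the final visit, 3, 6 and 12 months, with baseline PRTEE in the model, patients analysed as randomised and no listwise deletion. The 12-month between-arm contrast is the primary result. State the covariance structure and the small-sample degrees of freedom, and say how patients with only a baseline score are counted. Multiple imputation by arm from the same visits, covering all 44 patients and specified in advance, is an acceptable equivalent.
- **Sensitivity:** one missing-not-at-random analysis, with imputed BFR-arm values shifted by 0 to 10 PRTEE points to find where the conclusion changes.
- **Supporting only:** complete case.

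The cost is SAP wording and a little more analysis work; no new patients, data or software. The primary would rest on a missing-at-random assumption, which cannot be verified; the sensitivity analysis shows how far the conclusion depends on it.
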